Randomization: Immediately after completing baseline assessment, small block randomization (via REDCap) will create groups balanced on age and on the proportion who identify as nHBAM. We estimate that 90% of those enrolled will be nHBAM. 72 participants will provide sufficient power for the analyses (see Data Analysis). Recruitment will continue until 72 nHBAM are enrolled.

Format: Immediately after randomization, participants (adolescents and parents/caregivers) in the active (MySTYLE) condition will receive two secure, HIPAA compliant texts or emails to their mobile phones or preferred indicated device each week for eight weeks and each text/email will contain a link to new media content (overall, at least 120 minutes of multimedia time is planned, not including participant replays, which is comparable to our interactive DVD and to an online RCT conducted by Mustanski and colleagues). (9) The weekly content, as well other content and interactive materials, will be available on their condition's secure website. All nHBAM and enrolled parents/caregivers will each have their own links with separate, but parallel, content (see Figure below in Intervention Conditions). Those participants assigned to the waitlist will be eligible to participate in MySTYLE after they have completed their 2- and 4-month assessments. They then will receive two secure, HIPAA compliant texts or emails to their mobile phones or preferred indicated device each week for eight weeks and complete further assessments at 6 and 8 months. If those enrolled in the waitlist choose to participate in MySTYLE, they will have the opportunity to include their parent mid-intervention. During the 4 months that the participant is on the waitlist, study staff will not engage with the parent.

Intervention fidelity and usage: The twice-weekly video/graphic content will be embedded in the participant's unique REDCap link, providing data on the number of videos viewed by each participant. The participant will not proceed to the next web page (containing options for their weekly practice, etc.) until the video has fully played, but it may be paused and resumed later. The videos/graphics will be posted on the website for repeat viewing. Analytics will be collected on the number of minutes enrolled nHBAM spend viewing project materials, the content accessed, and the number of times any one video was re-played.

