Analysis Plans for Aims 1 and 2 – see Formative Work earlier in this application. Analysis Plan (Aim 3). Enrollment will continue until 72 nHBAM are randomized Hypothesis: Among the 72 families enrolled with nHBAM, those in the MySTYLE will have fewer condomless sex acts (CSAs), a less onset of sexual activity, and greater HIV testing rates, compared with those in the waitlist control by the 4-month assessment. Further, those randomized to MySTYLE will have significantly greater levels of HIV prevention knowledge, more favorable attitudes toward HIV prevention, greater HIV prevention self-efficacy, and more effective family practices at 2- and 4-month assessments. Data will be aggregated across follow-up assessments and analyzed using generalized linear models. CSAs will be analyzed using a negative-binomial model, which will account for over-dispersion due to zero-inflation. HIV testing during the follow-up period will be assessed using a logistic model. Knowledge, attitude, and HIV risk scores will be evaluated at baseline, 2, and 4 months using linear mixedeffect models, which will account for the three assessments being nested within individuals, and will help mitigate bias due to missing data. (100, 101) We will test for differences in linear change over time between groups on each outcome variable. For HIV testing outcome, we will evaluate difference between conditions in the proportion of participants who engaged in HIV POC test. Propensity scores (i.e., inverse probability of treatment weighting) will be used to account for any imbalance in baseline characteristics between conditions. (102) Note that the research uses small block randomization based on age and sexual experience to reduce group imbalance. Intervention acceptability will be determined at the 2-month assessment using the Aim 2 criteria of mean scores ≥ 24 on the CSQ and ≥30 on the SEF.

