Power. Although pilot studies are not typically powered for significance testing, (103) the RCT of 72 will nonetheless provide a "signal" of impact regarding major outcomes – e.g. CSAs, HIV testing, parenting practices. We conservatively assume that retention of 72 participants over 4 months is 85%, based on previous trials. Power analyses for knowledge, attitudes, and family practices were run with Optimal Design 3.01⁽¹¹⁷⁾ and assumed 3 assessments nested within cases. The HLM analyses with alpha of 0.05 and power 0.80 will be able to detect an effect size .41 SD for change in the scale score outcomes. If the alpha is 0.1 (as is appropriate in exploratory research), then power is 0.80 to detect an effect size of .36 SD, so this study should detect meaningful "signals" of impact. Power estimates for the behavioral counts were estimated using Mplus simulation utility using estimates from [name] previous prevention trials with adolescents. As expected, the study will be powered to detect medium to large effect sizes (rate-ratios/odds ratios ranging from 2.67 to 6.05). These combined data (scale scores, behavior outcomes, acceptability) will be used to revise intervention content and procedures, as indicated, and to prepare for a larger, definitive efficacy trial.

Protection of Human Subjects and Safety Monitoring Plan

Please note: In the Human Subjects section, we use the term **parent** to refer to the legal guardian of the adolescent and **caregiver** to refer to any family member or trusted, involved adult. Parent engagement in the RCT phase is desirable; however, caregiver engagement is also acceptable to meet the needs of the intended intervention (MySTYLE).

Human Subjects Involvement, Characteristics and Design

The program will be described in recruitment and advertisements as building healthy adolescent relationships and acceptance of straight and gay adolescents. Parents will be approached for consent after the teens have indicated an interest in the project, which will not reveal the adolescent's sexual orientation or behavior, only an interest in participating.

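### The slope test for youth scale scores names no adjustment for each scale's own baseline; fitted in the usual way it is valid, but adjusting would cut the variance by about 8–10% at the correlation the plan's power figure implies

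*Combined protocol and SAP*

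**What the plan says.** All of this is in the combined protocol and SAP.

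- **Model (Data Analysis Plan, Aim 3).** The three-visit analysis is introduced as "Knowledge, attitude, and HIV risk scores will be evaluated at baseline, 2, and 4 months using linear" (the sentence is cut here; the method is a mixed-effects model). The test is then given: "We will test for differences in linear change over time between groups on each outcome variable". Baseline is therefore the first of three repeated outcomes. The text does not say whether the model has a group term at baseline (arm means free) or a common baseline mean, and it names no baseline-score covariate.
- **Handling of imbalance (same section).** Inverse probability of treatment weighting is planned for baseline imbalance. No covariate list is given.
- **Hypothesis (same section).** It concerns differences in levels at the 2- and 4-month assessments.
- **Timing (RCT Phase, Randomization).** "Immediately after completing baseline assessment, small block randomization (via REDCap"). Youth baseline scores therefore precede allocation.
- **Power.** For these scores the plan claims: "The HLM analyses with alpha of 0.05 and power 0.80 will be able to detect an effect size .41 SD for change in the scale" (the sentence is cut here). At alpha 0.10, "then power is 0.80 to detect an effect size of .36 SD". No correlation, variance component or covariance structure is stated.

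**The concern.** A mixed model with group, time and group-by-time terms estimates a separate baseline mean for each arm. The slope difference then carries the full baseline noise of a change score. Because youth are randomised after baseline, the true baseline difference is zero, and estimating it freely spends information for nothing. Adjusting for the baseline score, or giving both arms one baseline mean, uses the same data and gives a smaller expected variance.

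At stake is the precision of the youth knowledge, attitude, self-efficacy and family scales. Aim 3 is meant to produce effect sizes for planning a larger trial, so the width of those estimates is a main quantitative product of a 72-person pilot.

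**Working it through.** **Inputs**
- Number randomised: 72 ("Enrollment will continue until 72 nHBAM are randomized").
- Allocation: no ratio is stated; 1:1 is assumed.
- Retention: "We conservatively assume that retention of 72 participants over 4 months is 85%, based on previous trials", so 0.85 × 72 = 61.2.
- Alpha 0.05 (two-sided assumed) and power 0.80: 1.960 + 0.842 = 2.802.
- Visits at 0, 2 and 4 months.
- Correlation rho and covariance structure: not in the documents. Compound symmetry with rho from 0.5 to 0.84 is assumed. The effect is read as the month-4 difference in change, in SDs of a single score.

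**Step 1. The plan's own figure.** With baseline means free, the detectable effect is

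MDE = 2.802 × √[(4/N) × 2(1 − rho)].

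This cannot be evaluated without rho, so solve it for .41:
- N = 72: 2.802 × √(4/72) = .660; rho = 1 − (.41/.660)²/2 = 0.81.
- N = 61.2: 2.802 × √(4/61.2) = .716; rho = 1 − (.41/.716)²/2 = 0.84.

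The two stated effects agree with each other: .41 × (1.645 + 0.842)/2.802 = .364, against the stated .36.

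**Step 2. Gain from using the baseline.** Variance relative to the free-baseline slope, under compound symmetry:
- visit as a category, month-4 contrast, own baseline as covariate: (1 + rho)/2;
- linear time with a common baseline: 2(1 + 2rho)/(5 + rho).

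| rho | MDE, free baseline (N = 61.2) | Reduction, categorical visit | Reduction, linear common baseline |
|---|---|---|---|
| 0.5 | .72 | 25% | 27% |
| 0.6 | .64 | 20% | 21% |
| 0.7 | .55 | 15% | 16% |
| 0.81 (implied, N = 72) | .44 | 10% | 10% |
| 0.84 (implied, N = 61.2) | .41 | 8% | 8% |

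At the implied correlations the detectable effect moves from .41 to .41 × √0.90 = .39 or .41 × √0.92 = .39. Power at .41 SD rises from 80% to about 83–84%.

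**Step 3. Other covariance structures.** For the linear common-baseline model, first-order autoregressive correlation gives reductions of 38% at rho 0.5 and 15% at 0.837. The random-slope examples tried gave 5–21%.

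**Step 4. Does the planned weighting already deliver this?** Two simulations used 72 participants with complete data. Variance is relative to the unadjusted change comparison.

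With only the scale's own baseline in the propensity model (3,000 replicates):

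| rho | Weighting | Own-baseline covariate |
|---|---|---|
| 0.5 | 0.75 | 0.75 |
| 0.7 | 0.87 | 0.86 |
| 0.837 | 0.93 | 0.93 |

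With several scales' baselines in one propensity model (2,000 replicates, correlation between scales 0.3 assumed):

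| rho | 5 scales | 10 scales | 15 scales |
|---|---|---|---|
| 0.5 | .87 | .99 | 1.14 |
| 0.837 | 1.04 | 1.11 | 1.43 |

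Table 1 lists roughly ten or more youth measures. One propensity model covering them all would lose the gain.

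**Step 5. Which baseline-adjusted model?** Fixing a common baseline while keeping linear time leans harder on linearity. The intervention ends at week 8, and the measures section itself anticipates effect decay. Under compound symmetry, if the effect plateaus at month 2, that model overstates the month-4 effect by a factor 6/(5 + rho): 1.09 at rho 0.5 and 1.03 at 0.84. If the effect halves by month 4, the overstatement is 27% and 8%. The free-baseline slope has no such bias at month 4. Categorical visit also avoids it and keeps nearly all the gain (Step 2).

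**The case against.** The strongest reply is that the plan is silent rather than wrong. It never says that baseline means are free by arm, and a common-baseline fit is not excluded. That is true, so the point is conditional on the usual fit.

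A reader might infer that the plan makes no use of baseline comparability. The documents do not support that: the plan has blocked randomisation to limit imbalance and propensity weighting for what remains. Weighting with the scale's own baseline recovers most of the gain, provided the standard errors account for the estimated weights. What stands is that the covariates are not listed, and that one propensity model for many scales does not deliver it.

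A reader might also take 27% as the expected gain, or about 27% more participants (1/0.786, at rho 0.6). Both rest on assumed correlations. At 0.5 and 0.6 the slope test's detectable effect would be .66–.72 and .59–.64 SD, which cannot be squared with the stated .41.

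Finally, this is a pilot looking for a signal, and .02 SD is small. That limits the weight of the point but does not remove it, since the change needs no new data. A correlation of 0.84 on every scale over four months may also be optimistic. If it is lower, the gain is larger and .41 SD is out of reach.

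**Conclusion.** The point holds as a matter of efficiency, not validity. As ordinarily fitted, the slope comparison is unbiased under randomisation but gives up precision that the pre-randomisation youth baselines could supply. The expected gain is about 8–10% of the variance (.41 to about .39 SD). This rests on compound symmetry, 1:1 allocation, a two-sided test and the correlation backed out of the plan's own power figure. It would reach 25–27% only at a correlation near 0.5, which the documents do not give.

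The gain cannot be claimed for parent or caregiver scales. The parent enrolment section lets parents join at entry, mid-intervention or after it. The Format section says staff do not engage waitlist parents for 4 months. Their first scores may therefore follow randomisation and be affected by arm.

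**What to change.** - **Primary model, youth-reported scales only.** A mixed model of the month-2 and month-4 scores with visit as a category, group-by-visit effects and that scale's own baseline as covariate. A common-baseline model with categorical visit is an acceptable alternative. Do not use the linear-time common-baseline version.
- **Reporting.** Give the month-2 and month-4 differences with intervals. This also matches the stated hypothesis, which is about levels at those visits.
- **Weighting.** Keep it as a sensitivity analysis, with the propensity covariates listed in advance.
- **Parent scales.** Leave them out of this change where the first score may come after randomisation.

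The cost is a sentence or two in the analysis plan, with no new data and no participant burden. The one small downside is that a single slope test per scale becomes two visit-specific contrasts.

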Digital consent, enrollment, and follow-up: In light of the COVID-19 outbreak, several of our recruitment sites (i.e. CBOs, clinics, and schools) have either closed or are limiting nonessential visits. This limitation severely impacts our ability to recruit and enroll potential participants in-person for the RCT phase of this project. We are proposing to offer digital consent and enrollment via HIPAA-compliant platforms (i.e. DocuSign, HIPAA-compliant video conferencing platforms). nHBAM identified as eligible, based on an online REDCap screener, will be asked if they would like to be contacted by study staff. Those that indicate they would like to be contacted will then be asked to provide their name, email address, and phone number. UMMC research assistants will follow up with interested parties by phone or email. Those who wish to participate will receive a DocuSign consent form via email from the UMMC research assistant and will be given the opportunity to participate in a video conference call (via HIPAAcompliant video conferencing platform with the UMMC research assistant to review the consent form. The DocuSign consent form will outline study aims and procedures and contains language regarding the risks/benefits of participating in a research study. The online survey data will be de-identified and kept in a password-protected participant log on a secure server. Participants will be given ample time to consider risks of participation and will have the opportunity to ask questions during the video conference. Participants will also be reminded that study participation is voluntary and that refusing to participate or withdrawing from the study at any time will not result in any negative consequences. For the remaining follow-up appointments (at 2- and 4-months, and additionally at the 6- and 8-month appointments for waitlist control participants) participants will be emailed their online REDCap surveys and will receive online gift cards for each completed survey. At the 4-month appointment, nHBAM will be offered a home HIV testing kit, that will be mailed to them by UMMC, in lieu of an in-person HIV test.

Parent or caregiver enrollment: The RCT allows nHBAM into the program before parent/caregiver involvement is requested (with a waiver of parental consent for those under 18) and then prepares nHBAM to safely involve their parent, if possible. More detailed information on the process is shown in the schematic below. nHBAM aged 18 or older

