Nonheterosexual orientation: Because youth are enrolling in a project to promote Straight – Gay Acceptance, we anticipate that nearly all will be nonheterosexual, that is they will identify with at least one of the following categories: a) have had at least one non-coercive intimate sexual experience (e.g., prolonged kissing, oral sex, anal sex) with a male, b) expect to someday have a male sex partner, c) sexually aroused by and attracted to males, or d) selfidentify as gay, bisexual, gender-queer, or other term that is not heterosexual. In addition to determining feasibility and acceptability of MySTYLE, the purpose of the small RCT conducted is to determine effect size differences in knowledge, attitudes, and behaviors. Given the reality of effect decay and the constraints of the R34, we will use only two follow-up assessments at 2 and 4 months after baseline. Participants assigned to the waitlist control condition will also complete assessments at 6 and 8 months. Scale score outcomes include relevant knowledge (e.g. HIV/ STIs), attitudes (e.g. internalized stigma, condom attitudes) and behavior (e.g. prevention self-efficacy, parental monitoring of teens' activities and companions, and practice exercises) (see Appendix 2). Scales will be adapted for nHBAM from those used in STYLE or by our investigators. Table 1 summarizes our central measures, as a function of the Social Personal Framework, and others may be added as needed based on our formative work. **Behavioral outcomes** are: (1) the number of condomless sex acts during the follow-up period. (2) the rate of onset of sexual activity and (3) the acceptance of an HIV test. Sexual behaviors. HIV testing history and STI history will be assessed in a computer-assisted self-interview designed specifically for use with adolescents and using branching logic so that they only answer items that are relevant. (76-78) As a dependent variable, adolescents will be offered a free point-ofcare (POC) HIV test at 4. Also, self-report of prior HIV and STI testing will be assessed. Those who are not yet sexually active may decide against HIV testing and we will analyze the differences in testing rates separately based on self-report of sexual activity. Our outcome is testing, rather than the HIV or STI results because rates of infection will likely be low at this age, although the study will provide data on this issue in our high-prevalence city of Jackson, MS. Intervention content acceptability: At 2 or 6 months, depending on assigned condition, adolescents will complete the CSQ (see Year 2) to assess relevance and utility of the content and to aid in refinement of the intervention, if needed, prior to a subsequent, larger RCT.

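### The HIV-testing comparison counts only point-of-care tests, although a mailed home kit may replace the in-person test at month 4

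*Combined protocol and SAP*

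**What the plan says.** The Measures for the Randomized Trial section of the protocol lists three behavioural outcomes, the last being "3) the acceptance of an HIV test". It adds "Our outcome is testing, rather than the HIV or STI results" and ties the outcome to one offer: "As a dependent variable, adolescents will be offered a free point-ofcare (POC) HIV test at 4" (months, from the context). It does not mention a kit. It also collects self-reported prior testing, and says of the testing comparison that "we will analyze the differences in testing rates separately based on self-report of sexual activity", without giving the time at which activity is reported.

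The Analysis Plan (Aim 3) describes the outcome in three ways:
- The hypothesis predicts "greater HIV testing rates, compared with those in the waitlist control by the 4-month assessment".
- The model sentence says "HIV testing during the follow-up period will be assessed using a logistic model".
- The comparison sentence says "we will evaluate difference between conditions in the proportion of participants who engaged in HIV POC test".

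The kit enters under Digital consent, enrollment, and follow-up. The month-4 rule there reads: "nHBAM will be offered a home HIV testing kit, that will be mailed to them by UMMC, in lieu of an in-person HIV test". The human-subjects part repeats this under RCT digital consent, enrollment, and follow-up. The randomised-trial paragraph under Sources of Material places the POC test at the in-person 4-month visit and gives the kit as the other option.

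Two further places still describe in-person testing alone. Research Material Obtained from Living Human Subjects lists POC results as the only HIV test data. The Emotional Distress section has the site project director carry out all HIV testing.

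**The concern.** The protocol gained a second route to the month-4 test when COVID-19 limited visits, but the sentence that scores the outcome still names the first route only. If an analyst follows that sentence with all participants in the denominator, kit users fall outside the numerator.

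HIV testing is one of three behavioural outcomes, and its effect size is meant to inform the larger trial. The documents report closed sites and emailed follow-up surveys, so kit use may be common, but they give no share. In arms this small, a few reclassified youths change the estimate visibly.

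The plan also leaves three different events in play: accepting the month-4 offer, any testing during follow-up, and having a POC test. It does not say which governs, so the choice could be made after the data are seen.

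**Working it through.** **Does the text treat kit and POC as one route or two?** The Digital consent section makes the kit a substitute for the in-person test. The Sources of Material paragraph ties the POC test to the in-person visit and offers the kit as the alternative. They are therefore two routes. No passage says that accepting, using or reporting a kit counts as a POC test.

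**Inputs.** The documents give 72 randomised and 85% retained over 4 months (Power section). Allocation is not stated, so 1:1 is assumed. Testing rates and kit shares are not given, so the values below are assumptions. The Power section's detectable ratios for behavioural outcomes (2.67 to 6.05) came from a simulation whose inputs are not shown. They cannot be reproduced, and nothing here disputes them.

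**Shift per youth.**
- All randomised: 72 / 2 = 36 per arm, and 1 / 36 = 2.8 points.
- Retained: 72 × 0.85 = 61.2, or 30.6 per arm, and 1 / 30.6 = 3.3 points.
- A net imbalance of three kit users: 3 / 36 = 8.3 points to 3 / 30.6 = 9.8 points, in either direction.

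**Equal kit share k among acceptors.** The POC-only rate is p × (1 − k) in each arm. The risk difference is multiplied by (1 − k), and the risk ratio is unchanged. With POC-only rates a (MySTYLE) and b (waitlist), OR = [a / (1 − a)] / [b / (1 − b)].

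| Kit share | Acceptance 60% vs 30% | Acceptance 50% vs 35% |
|---|---|---|
| 0 | 30 points, OR 3.50 | 15 points, OR 1.86 |
| 10% | 27 points, OR 3.17 | 13.5 points, OR 1.78 |
| 30% | 21 points, OR 2.72 | 10.5 points, OR 1.66 |
| 50% | 15 points, OR 2.43 | 7.5 points, OR 1.57 |
| 70% | 9 points, OR 2.22 | 4.5 points, OR 1.50 |

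Worked line for 60% vs 30% at k = 50%: 0.30 vs 0.15, difference 0.15, OR = (0.30 / 0.70) / (0.15 / 0.85) = 2.43. If every acceptor used a kit, both arms would score zero and there would be nothing to compare.

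**Other patterns, from the same 60% vs 30%.**
- Equal numbers of kit users, 10 points off each arm: 50% vs 20%. The difference stays at 30 points, the OR rises from 3.50 to 4.00, and the risk ratio rises from 2.0 to 2.5.
- Kit share 75% in MySTYLE and 25% in waitlist: 15% vs 22.5%, OR 0.61. The direction reverses.
- Kit share 25% in MySTYLE and 50% in waitlist: 45% vs 15%. The difference is 30 points and the OR is 4.64.

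**No true effect**, 50% in each arm, kit share 50% in MySTYLE and 25% in waitlist: 25% vs 37.5%, OR 0.56.

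**The case against.** The strongest reply is that no passage assigns a non-tester code to kit users. The Measures section speaks of accepting a test and of testing as the outcome, and the model sentence refers to testing without naming a type. A kit offered in place of the in-person test is most naturally a second route to the same outcome. This stands as evidence of intent: any test was probably meant. It does not remove the comparison sentence, which is the only one that says what is counted and which names POC alone.

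It is also fair to say that the shift is modest against sampling error. At 60% vs 30% with 30.6 per arm, the standard error of the difference is √[(0.60 × 0.40 + 0.30 × 0.70) / 30.6] = 0.121, about 12 points, so the three-youth shift is below one standard error. But the trial exists to supply effect sizes, and this error is avoidable.

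Three stronger readings are tempting, and the documents do not support them:
- A reader might infer that kit users will be miscoded. The text shows a definition that was not updated, not a settled coding decision.
- A reader might infer that equal kit use always pulls the effect toward the null. That holds for an equal share among acceptors. Equal numbers can raise the odds ratio, as shown above.
- A reader might infer that capture of kit use differs by arm because only waitlist youths have 6- and 8-month surveys. The hypothesis fixes the comparison at the 4-month assessment, and nothing proposes scoring testing from the later surveys.

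**Conclusion.** The point holds as a mismatch between the scoring sentence and the permitted test routes. Taken literally, the Aim 3 comparison leaves kit users out of the numerator of an outcome that the Measures section defines more broadly. Confidence in the mismatch is high. The size and direction of any bias are unknown, because they depend on acceptance rates and kit shares that the documents do not give. The per-youth figures of 2.8 to 3.3 points rest on 1:1 allocation, and the odds ratios are illustrations only. The wording should be corrected before the outcome is analysed; the design itself is not undermined.

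A secondary point concerns the split by sexual activity. The plan hypothesises that MySTYLE affects onset of sexual activity. If activity is taken from follow-up reports, the subgroups are formed after randomisation by something the intervention may change, and the arms within a subgroup are no longer protected by randomisation.

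**What to change.** In the Analysis Plan (Aim 3), replace the POC sentence with one defined outcome: acceptance of the study's month-4 HIV test offer by either route (in-person POC or home kit), yes or no, logged by staff in the same way in both arms with the route recorded, and compared by randomised arm. State how youths not reached at month 4 are coded, since the choice between 36 and 30.6 per arm depends on it.

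Tabulate route by arm and show POC only as a sensitivity analysis. Keep self-reported testing over months 0 to 4 as a separate secondary outcome. In the Measures section, split the testing analysis by the baseline report of sexual activity.

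Reconcile the Measures section (POC offer only), the list of research material (POC results only) and the Emotional Distress section (testing by the project director only) with the three places that allow the kit.

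The cost is wording and a staff log of offer, answer and route. The protocol already provides for staff forms in REDCap, and UMMC mails the kits, so no new visit or survey is needed. The drawback is that accepting a kit is a weaker act than being tested on the spot, which is why route and POC-only results should be shown.
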